9.2. Setting

The assessment surveys will be executed as soon as 12 months but no later than 18 months from launch of the product in Germany, the UK (if product uptake does not allow for participation, another comparable EU country will be selected), and a third EU country to be determined. Countries will be selected based on a sufficient number of prescribers and volume of prescriptions to allow for a successful enrolment of HCPs and patients. Pan-European diabetes treatment guidelines issued by professional organizations such as European Association for the Study of Diabetes (EASD; Inzucchi et al. 2015) and the European Society of Cardiology for the management of patients with diabetes, such that the difference in clinical practices in different EU countries should be negligible (ESC Task Force 2013). Therefore, selection bias will be largely prevented due to common clinical practice, standardized messaging, and survey implementation. The timing of the initiation of the survey depends on the product launch dates and the product uptake in each country.

The target population in each selected county will receive the same risk communication, to be provided in their official national language. Additionally, the same survey will be used in all 3 countries in order to test the target population on the same key safety messages. As such, variability of survey results based on geography is not anticipated and therefore 3 countries will be representative of the EU.

The UBC will administer the surveys to the study populations who respond to the invitations to participate in the study. Every effort will be made to ensure the samples participating from each country in the survey will be proportional to the expected eligible population among participating countries. The EDC system will be programmed to ensure desired distribution by requiring a minimum number of eligible participants from each country.

HCPs:

Surveys targeting eligible HCPs will be administered via the Internet, which will allow respondents to participate at a time and location that is convenient for them, and by telephone, to allow participation of respondents who do not have Internet access. Both modalities will offer the same survey.

Eligible HCPs will receive an invitation letter via email if an email address is available, or a letter in the postal mail inviting them to participate in the survey. The invitation letter (Appendix I.2) will include: an overview of the rationale for the survey, information on how to access the survey online and by telephone, and a unique User Identification (ID) to ensure that the invitation is used only once.

HCPs in the applicable countries who are involved in the treatment and management of patients with diabetes will be invited to participate in the survey. The respondent population will include a mix of prescribers who have and have not prescribed Humalog 200 units/ml. The response rate will be monitored throughout the data collection period. Reminder notices will be sent via email and postal mail, and telephone calls will be made periodically to HCPs who have been invited

but not yet participated. The HCPs that complete the survey will be reimbursed for their time spent participating as governed by local laws and country regulations.

Patients:

Surveys targeting eligible patients will be administered via the Internet, which will allow respondents to participate at a time and location that is convenient for them, and by telephone, to allow participation of respondents who do not have Internet access or are not computer literate. Both modalities will offer the same survey.

Patients will be recruited via study packets that will be provided to HCPs due to privacy concerns in the EU. All HCPs who receive an invitation to participate in the HCP survey will also receive a study packet of patient invitations in the postal mail and a letter asking them to invite eligible patients to participate in the survey. The packet will contain 10 invitation letters to be distributed. The patient invitation letter (Appendix I.4) will include an overview of the rationale for the survey, information on how to access the survey online, the toll-free number for accessing the telephone survey, and a unique User ID to ensure that the invitation is used only once. The HCPs will not be asked to select specific patients based on eligibility criteria. HCPs will forward the patient invitations to their patients for whom they have prescribed Humalog 200 units/ml. In the event an HCP has prescribed Humalog 200 units/ml to more than 10 patients, the HCP will arbitrarily select 10 patients regardless of any additional eligibility criteria.

Notices will be sent and telephone calls will be made periodically to HCPs reminding them to invite patients to participate in the survey. During reminder telephone calls, feedback will be elicited regarding barriers to patient participation. If feedback is received showing that Internet and telephone modalities are barriers to survey completion, HCPs will be provided with paper versions of the survey. Each paper survey will include a postage paid envelope for returning the completed patient survey.

Patients who complete the survey will be offered reimbursement for their time spent participating as governed by local laws and country regulations.

If the rate of response is not sufficient to reach the goal population within the planned survey period, Lilly may employ additional measures in an effort to complete the sample, such as but not limited to, extend the survey period, increase the payment amount provided to stakeholders as allowed by local laws and country regulations, increase the frequency of or change the method of outreach to HCPs, and allow for respondents to schedule an appointment to take the survey over the phone or provide the means to participate by paper survey.

To ensure comprehension of the invitations and surveys, all of the outreach will be conducted in the official national language. The survey and invitation as well as any reminder letters will be translated by a certified translation vendor.

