4.10. Milestones

The study will be implemented within 12 to 18 months of product launch in the UK (if product uptake does not allow for participation, another comparable EU country will be selected),

**Non-Interventional Study Protocol
for Humalog 200 units/ml KwikPen
Version 1.0**

Germany, and one additional EU country. The timing and countries chosen is dependent on launch dates and the uptake of the product in each country. Findings from the surveys will be reported to regulatory authorities as required.

5. Amendments and updates

Not applicable.

6. Milestones

Milestone	Planned Timeline*
Start of data collection	Within 12-18 months from product launch in the applicable country, depending on launch dates and the uptake of the product in each country.
End of data collection	When the desired number of surveys have been completed.
Registration in the EU Post-Authorisation Safety Studies (PASS) register	Prior to start of data collection
Final study report	Within 12 months after the end of data collection

*The study will be initiated after the distribution of the additional risk minimisation measures) across the 3 study countries and protocol review by PRAC. Therefore, the planned timeline is contingent upon the date of the approval of the RM tools by the local Health Authorities.

7. Rationale and background

Diabetes, especially T2DM is increasing in global prevalence and associated economic and humanistic burdens. Despite tangible improvement in disease management, poor glycaemic control remains a problem in individuals with diabetes (Inzucchi et al, 2012). Diabetes management guidelines recommend early initiation of insulin therapy in individuals with poor T2DM control or those with poor response to other anti-diabetes medications (Petznick A, 2011; ADA, 2014). In addition, insulin resistance and progressive loss of pancreatic beta-cell function are prodromal features of T2DM, which partially contribute to the need for high-dose insulin therapy—worldwide, about 30% of patients using basal insulin require more than 60 units daily (Gough et al, 2013), and approximately half of patients with T2DM will eventually require insulin to manage their diabetes (Jabbour, 2008).

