Humalog 200 units/ml KwikPen is a prefilled and multi-dose pen-injector device (pen) that delivers by subcutaneous injection insulin lispro for the maintenance of normal glucose homeostasis in adults with diabetes mellitus. Compared to Humalog 100 U/ml, it contains the same number of units of insulin lispro in half the volume. Despite warning messages on the pen and in the instructions for use, results from Human Factors studies performed in the US showed that a small percentage of patients may choose to withdraw insulin from the pen cartridge with a syringe if faced with device malfunction. Anecdotal information also indicates that patients in the EU may transfer insulin lispro from the pen cartridge into an insulin pump. Because of these data and to further optimise the benefit-risk balance of the formulation, additional Risk Minimisation Measures beyond routine risk minimisation measures (are being implemented, including communications to HCPs and patients to minimise the risk of hypoglycaemia and/or hyperglycaemia associated with insulin transfer from the pen cartridge to an alternative administration device without concentration adjustment and dose adjustment when transferring from Humalog 100 U/ml to Humalog 200 units/ml KwikPen.

**Non-Interventional Study Protocol
for Humalog 200 units/ml KwikPen
Version 1.0**

The additional risk minimisation measures include a DHPC that will be distributed to all physicians and nurses who are expected to be involved in the treatment and management of patients with diabetes and, where required, all pharmacists who are expected to dispense Humalog 200 units/ml KwikPen (HCPs). A patient communication document will be distributed to HCPs targeted for the DHPC. The DHPC will ask the HCPs to provide the patient communication to patients receiving their initial prescription of Humalog 200 units/ml KwikPen. Where approved, a web address link to the patient communication may also be provided in the DHPC to allow either printing of the communication during the patient visit or provision of the link to the patient to enable the patient to directly access the communication.

8. Research question and objectives

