9.4.1. Data collection process

The survey start date will be within 18 months from product launch in the individual countries. This date will vary by country based on market uptake. Survey data collection will be closed when the desired number of surveys have been completed.

The Internet survey will be self-administered. For the telephone survey, a trained interviewer from the Survey Coordinating Centre will conduct the telephone interviews using a Computer-Assisted Telephone Interviewing (CATI) programme and enter participant responses directly into the EDC while in conversation with the respondent. Questions are programmed to ensure that they are asked in the appropriate sequence and skip patterns are clearly indicated.

Respondents cannot go back to a question once the question has been answered and they cannot

skip ahead. Statements requiring response and response options presented in a list are randomised to minimise positional bias. Paper surveys, if employed, will have instructions to guide respondents through the survey correctly and a Call Centre Associate (CCA) will enter the responses into the EDC verbatim from the paper survey received.

Follow-up reminder process

HCPs:

The database of invited HCPs will be routinely updated with responders and after each mailing, the database will be cross-checked with any correspondence that had an invalid address, bounced back or had incorrect contact details. The target sample for survey reminders is HCPs who received the invitation (that is, no reason for not receiving, such as invalid address) but did not respond within 2 weeks from initial mailing. Using the updated database, at least one reminder will be sent to the sample defined above. The total number of reminders will be based on the response rate at predefined recruitment milestones identified by Lilly. The interval between the reminders will be approximately 2 to 3 weeks.

Patients:

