This survey should take approximately 15 minutes to complete. If you cannot complete the survey at this time, please return when you can. Once you begin the survey you will need to answer all questions; you will not be able to access the survey again if you exit.

Thank you in advance for your participation. Please note the application will time out after 30 minutes of inactivity.

If you are ready to begin the survey at this time, please click continue. If not, click Return Later.

Please note: Do not use the browser's back button during this survey.

[END WELCOME PAGE]

[BEGIN SCREENING QUESTIONS]

Please provide a response to all questions and statements.

1. Do you agree to take part in this survey about Humalog[®] 200 units/ml KwikPen[™]?
 - Yes
 - No **[TERMINATE]**

2. Have you been diagnosed with diabetes?
 - Yes
 - No **[GO TO Q9; TERMINATE AFTER Q12]**
 - I don't know **[GO TO Q9; TERMINATE AFTER Q12]**

3. How long have you had diabetes?
 - Less than 1 year
 - 1 – 5 years
 - 6 – 10 years
 - 11 – 15 years
 - More than 15 years
 - I don't know
 - I don't have diabetes**[GO TO Q9; TERMINATE AFTER Q12]**

4. Do you use injectable insulin to treat your diabetes?
 - Yes
 - No **[GO TO Q6; TERMINATE AFTER Q12]**
 - I don't know **[TERMINATE AFTER Q12]**
 - I don't have diabetes **[TERMINATE AFTER Q12]**

5. For how long have you been using injectable insulin to manage your diabetes?
- Less than 1 year
 - 1 – 5 years
 - 6 – 10 years
 - 11 – 15 years
 - More than 15 years
 - I don't know
 - I don't have diabetes/I don't use insulin **[GO TO Q9; TERMINATE AFTER Q12]**
6. Have you been prescribed Humalog 200 units/ml KwikPen at least once?
- Yes
 - No **[GO TO Q8; TERMINATE AFTER Q12]**
 - I don't know **[GO TO Q8; TERMINATE AFTER Q12]**
 - I don't have diabetes/I don't use insulin **[GO TO Q8; TERMINATE AFTER Q12]**
7. For how long have you been using Humalog 200 units/ml KwikPen?
- I have not used it yet
 - Less than 3 months
 - 3 – 6 months
 - 7 – 12 months
 - More than 1 year
 - I don't know

- I don't have diabetes/I don't use Humalog 200 units/ml KwikPen **[GO TO Q9; TERMINATE AFTER Q12]**
8. What type of insulin did you use prior to using Humalog 200 units/ml KwikPen?
- Humalog 100U/ml
 - Other 100U/ml insulin
 - I don't know/I don't remember
 - I don't have diabetes/I don't use Humalog 200 units/ml KwikPen **[TERMINATE AFTER Q12]**
9. What is your gender?
- Male
 - Female
10. What is the highest level of education you have completed?

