- Some secondary school (or EU equivalent) or less
 - Finished secondary school
 - Some university or completed technical/trade school
 - Graduated university
 - Post graduate studies
 - Prefer not to answer
11. In what country do you live?
- [DROP-DOWN LIST INPUT WITH COUNTRIES TABLE]**
12. Which of the following groups best describes your age?

- Under 18 **[TERMINATE AFTER Q12]**
 - 18 – 29
 - 30 – 39
 - 40 – 49
 - 50 – 59
 - 60 – 69
 - 70 or older
 - Prefer not to answer **[TERMINATE AFTER Q12]**
13. Have you or any of your immediate family members ever worked for Eli Lilly and Company (Lilly), United BioSource Corporation (UBC), or the European Medicines Agency (EMA)?
- Yes **[TERMINATE]**
 - No
 - I don't know **[TERMINATE]**

[END SCREENING QUESTIONS]

[BEGIN SURVEY CONTENT]

[PREAMBLE 2]

The following questions are about Humalog 200 units/ml KwikPen.

14. Please answer True, False, or I don't know for each of the following statements about Humalog 200 units/ml KwikPen.

	[RANDOMISE LIST]	True	False	I don't know
A	Humalog 200 units/ml should only be injected using the			

prefilled KwikPen device in which it is supplied.

- B Your dose of insulin does not need to be converted when changing from one strength of Humalog to the other (for example, changing from Humalog 100 U/ml to Humalog 200 units/ml KwikPen).

15. Please answer Yes, No, or I don't know for each of the following statements about the patient communication titled *IMPORTANT SAFETY INFORMATION FOR Humalog 200 units/ml KwikPen (insulin lispro)*.

- | | Yes | No | I don't know |
|---|-----------------------|-----------------------|-----------------------|
| 
[RANDOMISE LIST]
 
[DISPLAY ONLY IN [ENTER COUNTRIES THAT DO NOT HAVE WEBSITE]]The first time I was prescribed Humalog 200 units/ml KwikPen, my doctor or nurse provided me with a paper copy of IMPORTANT SAFETY INFORMATION FOR Humalog 200 units/ml KwikPen (insulin lispro).
 |  |  |  |
| 
A [DISPLAY ONLY IN [ENTER COUNTRIES THAT HAVE WEBSITE]]The first time I was prescribed Humalog 200 units/ml KwikPen, my doctor or nurse provided me with a paper copy or told me to access the website to view IMPORTANT SAFETY INFORMATION FOR Humalog 200 units/ml KwikPen (insulin lispro).
 |  |  |  |

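### The launch-based survey window is not reconciled with the separate distribution condition, so any patient first prescribed before distribution counts against receipt of a document not yet available

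*Protocol*

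**What the plan says.** **Timing.** Section 9.2 states: "The assessment surveys will be executed as soon as 12 months but no later than 18 months from launch of the product". Section 9.4.1 repeats the upper limit: "The survey start date will be within 18 months from product launch in the individual countries". The Section 6 milestone table also counts from launch. The footnote to that table adds a different condition: "The study will be initiated after the distribution of the additional risk minimisation measures) across the 3 study countries and protocol review by PRAC". It continues that "the planned timeline is contingent upon the date of the approval of the RM tools by the local Health Authorities". No distribution date is given, and neither is an interval from launch to distribution or from distribution to survey.

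**Hand-over and receipt.** Under Section 7, the patient document is tied to the start of treatment: "The DHPC will ask the HCPs to provide the patient communication to patients receiving their initial prescription of Humalog 200 units/ml KwikPen". The patient receipt endpoint in Section 9.1 refers to the same moment, as does Q15A of the patient survey (Appendix I.3): "The first time I was prescribed Humalog 200 units/ml KwikPen, my doctor or nurse" gave the document or, where a website exists, pointed to it. The answers are Yes, No and I don't know.

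**Who is asked.** Section 9.2.1 and screening item Q6 admit any adult with diabetes who has ever been prescribed the product, with no limit on when. Q7 asks "For how long have you been using Humalog 200 units/ml KwikPen" in bands: not used yet, under 3 months, 3–6 months, 7–12 months, and more than 1 year.

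**Interpretation.** Section 9.9 reads reported non-receipt as dissemination that was not optimal. It mentions forgetting as an alternative explanation, but not unavailability.

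**The concern.** Two clocks govern one survey. The launch clock decides when patients begin to accumulate. The distribution clock decides when a patient could first have been given the document. The footnote delays the start of the survey until after distribution but does nothing about the date of a respondent's first prescription.

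If the tools reached a country after the product did, the receipt percentage would mix two things: clinicians who had the document and did not pass it on, and clinicians who did not yet have it. Only the first says anything about the programme. The mixture could differ by country, because approval is local. More respondents would not help, because this is bias and not sampling error.

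The two rules could also collide. If distribution in the last country came more than 18 months after launch in the first, the all-countries condition and the 18-month limit could not both be met in that first country. The protocol does not say which prevails.

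**Working it through.** **1. The plan's own precision.** Section 9.5, Equation 1, with n = 280: half-width = 1.96 × √(p(1 − p)/280). For p = 50/60/70/80/90% this gives 5.86/5.74/5.37/4.69/3.51 points, which matches Table 1 (5.9/5.7/5.4/4.7/3.5).

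**2. Dilution.** Let p be true receipt among patients who could have been given the document, and s the share of respondents first prescribed before distribution. If none of the latter answers Yes,

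observed receipt = p × (1 − s).

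At s = 0 nothing changes. Observed receipt equals 50% at s = 1 − 0.50/p:

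| True receipt p | s at which observed receipt is 50% |
|---|---|
| 60% | 1 − 0.50/0.60 = 16.7% |
| 70% | 1 − 0.50/0.70 = 28.6% |
| 80% | 1 − 0.50/0.80 = 37.5% |
| 90% | 1 − 0.50/0.90 = 44.4% |

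**3. What lag would produce such a share.** The protocol gives neither the lag L nor the uptake curve, so both are assumed here. With the survey at T months after launch, uniform uptake gives s = L/T, and uptake that rises over time (cumulative starts proportional to t²) gives s = (L/T)². Observed receipt when true receipt is 70%:

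| Lag L | T = 12, uniform | T = 12, rising | T = 18, uniform | T = 18, rising |
|---|---|---|---|---|
| 0 months | 70.0% | 70.0% | 70.0% | 70.0% |
| 1 month | 64.2% | 69.5% | 66.1% | 69.8% |
| 3 months | 52.5% | 65.6% | 58.3% | 68.1% |
| 6 months | 35.0% | 52.5% | 46.7% | 62.2% |

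The shift runs from nothing to several times the largest half-width in Table 1.

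**4. Whether Q7 can separate these patients.** A band lies wholly after distribution only if its upper end is no more than T − L. Take L = 3. At T = 18, T − L = 15, so the band above 1 year straddles the date and must be dropped whole. Under uniform uptake that removes about 6/18 = 33% of patients, when only 3/18 = 17% started too early. At T = 12, T − L = 9, so the 7–12 month band straddles the date; dropping it removes roughly half, against a true 3/12 = 25%. Q7 also asks about time in use, not date of first prescription. It can serve as a conservative filter, but a wasteful one.

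**5. Price of the restricted denominator.** n = 280 × (1 − s). At s = 10%, n = 252 and the half-width at 50% is 1.96 × √(0.25/252) = 6.2 points. At s = 25%, n = 210 and it is 6.8 points, against 5.9 for all 280.

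**The case against.** The strongest objection is that the premise is unproven. The footnote orders the survey after distribution; it does not order distribution after launch. A reader might infer that some patients were certainly started before the document existed. The documents do not support that: if distribution came at or before launch, s = 0 and there is no bias. This stands, and it makes the point conditional.

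A reader might also infer that a share of about 17% reverses the study's conclusion. That figure assumes true receipt of 60%, close to the 50% line. The majority criterion in Section 9.1 is worded around awareness of key risks. Receipt is listed beneath it, and whether the threshold applies to receipt alone is unclear. The primary objective is understanding, and Q14 is put to every eligible patient regardless of receipt.

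Nor do the documents support extending the point to the healthcare professional results. Survey items Q19 and Q20 ask about present practice, and no interval between distribution and survey is stated from which to argue that the message had barely arrived. It is likewise too strong to say that gap patients can only answer No: Q15A offers I don't know, and recall is imperfect.

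Three further defences carry some weight. Section 9.2 gives enrolment reasons for waiting until uptake is adequate. Section 9.7 plans analyses by country and by length of use, which could show lower receipt among early starters. The footnote can be read as letting the timeline slip with approval. However, the length-of-use analysis is not linked to distribution dates and does not correct the pooled figure, and the 18-month limit in Section 9.2 carries no exception. Detailed displays may be left to the SAP, but a first-prescription date that the survey never collects cannot be restored there.

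**Conclusion.** The point holds in a limited, conditional form. The protocol sets a launch-based window and a separate distribution condition without reconciling them. Neither eligibility nor the questionnaire distinguishes patients first prescribed before distribution from those prescribed after it. Where a gap exists, patient receipt is understated by the factor (1 − s). The formula assumes that no gap patient answers Yes, so mistaken recall would make the loss somewhat smaller. The size cannot be fixed from the document, since s, the lag and true receipt are all unstated. Q15B, on whether the clinician offered to explain the document, is exposed in a similar but looser way, because it is not tied to the first prescription. Understanding (Q14) and the healthcare professional items are not materially affected. This is a low-cost improvement to make while the survey is still in draft; it does not invalidate the study.

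**What to change.** - **Timing.** State in Sections 6, 9.2 and 9.4.1 how the launch-based window and the distribution condition work together, and which prevails if both cannot be met.
- **Dates.** Record the date on which the measures were distributed in each country and give it in the report.
- **Survey.** Add a patient item on month and year of first prescription. If only Q7 is kept, count only the duration bands that lie wholly after distribution in that country.
- **Analysis.** Make receipt among patients first prescribed after distribution in their country the main receipt figure, with all patients as supportive. If distribution preceded launch everywhere, the two figures coincide.

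The cost is one extra question, with its own recall error, and a smaller denominator. The half-width at 50% rises from 5.9 to about 6.2 points at s = 10% and 6.8 points at s = 25%. Keeping 280 evaluable patients would instead need about 312 (280/0.90) or 374 (280/0.75) completed surveys.

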4.7. Data Sources

Structured, self-administered surveys comprised of closed-ended questions or statements with multiple response choices (that is, questions or statements asking the respondent to choose from a defined list of responses) will be used to collect the survey data from random samples of HCPs (Appendix 1.1) and patients (Appendix 1.3).

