9.4. Data sources

In this survey, data sources for HCPs may be Lilly's lists of HCPs who received the DHPC (in countries where local privacy regulations or standard practices allow this list to be provided to UBC) and/or UBC's HCP reference files or panels. From these data sources, random samples of HCPs will be invited to participate in the survey and to invite patients to participate in the survey.

Structured, self-administered surveys (Appendix I.1 and Appendix I.3) comprised of closed-ended questions or statements with multiple response choices (that is, questions or statements asking the respondents to choose from a defined list of responses) will be used to collect the survey data. The surveys will collect data on respondent characteristics and their responses to

the risk understanding questions. The data collected from the surveys will be used to inform the evaluation of the effectiveness of the risk minimisation measures.

The survey is designed to be completely voluntary and anonymous to prevent the collection of any personal identifying information from participants. Each participant will be given a unique code to access the survey. Each code is deactivated upon its use to prevent the code from being used to complete the survey twice. Each code is randomly assigned and not tracked; therefore, no identification of patients who have or have not responded can be performed. The participants do not have to actively ‘decline to complete the survey’. Therefore, there is no ability to track which participants are actively deciding to not complete the survey. This survey design encourages patient participation and answer honesty by ensuring that the responses are completely anonymous.

Each survey will begin with a screening module with questions to confirm eligibility. Depending on the answers to the screening questions, survey participation will either be terminated or continued. If ineligible, the respondent is immediately notified with a “thank you” message that survey participation has ended. If eligible, the respondent is allowed to continue survey participation.

HCPs:

Screening questions:

- Agreement to participate
- Involved in the management of patients with diabetes
- Prior or current employment by Lilly, UBC, or any national medical governing body, such as but not limited to EMA, MHRA, and BfArM
- Awareness of Humalog 200 units/ml KwikPen

Data on demographic characteristics:

- Age
- Sex
- Role at facility
- Facility type
- Country

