9.5. Study size

The target sample sizes for the HCP and patient populations are 280 completed surveys for each population. This sample size was determined based on the width of confidence intervals it will provide. [Table 1](#) shows 2-sided 95% confidence intervals based on the normal approximation to the binomial distribution ([Equation 1](#)) for a single sample of size of 280.

The samples will be divided by countries according to the distribution of eligible participants in each country. The EDC system will be programmed with country-specific limits to ensure desired distribution. Both unweighted and weighted results will be presented in the final report.

Equation 1.

$$95\%CI = Response\ Rate \pm 1.96 \left\{ \sqrt{\left[\frac{Response\ Rate(1-Response\ Rate)}{Sample\ Size} \right]} \right\}$$

Table 1. Sample size calculations

Sample Size	Observed Response Rate* (e.g. Knowledge)	2-Sided 95% Confidence Interval		
		Half-width	Lower Limit	Upper Limit
280	50%	5.9%	44.1%	55.9%
	60%	5.7%	54.3%	65.7%
	70%	5.4%	64.6%	75.4%
	80%	4.7%	75.3%	84.7%
	90%	3.5%	86.5%	93.5%

*Percentage of responders who correctly answered a question.

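### The patient survey is a two-stage sample through HCPs, but precision is planned for 280 independent responses and no cluster identifier is kept to measure or correct the difference

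*Protocol*

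**What the plan says.** Under Section 9.2, patients are recruited only through HCPs. Every HCP invited to the HCP survey also receives a packet of ten patient invitation letters to pass to patients for whom he or she has prescribed Humalog 200 units/ml. Where there are more than ten such patients, "the HCP will arbitrarily select 10 patients regardless of any additional eligibility criteria".

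Section 9.4 limits random drawing to the HCPs, who then invite patients. The abstract (Section 4.7) goes further and says that structured surveys "will be used to collect the survey data from random samples of HCPs (Appendix 1.1) and patients (Appendix 1.3").

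Section 9.5 sets one target for both surveys: "The target sample sizes for the HCP and patient populations are 280 completed surveys for each population". The basis is precision alone: "This sample size was determined based on the width of confidence intervals it will provide". Table 1 gives "2-sided 95% confidence intervals based on the normal approximation to the binomial distribution" "for a single sample of size of 280". It has no design effect and makes no distinction between HCPs and patients.

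On the access codes, Section 9.4 states: "Each code is randomly assigned and not tracked; therefore, no identification of patients who have or have not responded can be performed".

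**The concern.** Patients of one prescriber share what that prescriber handed out and said. Q15A in the patient survey (Appendix I.3) asks whether the doctor or nurse supplied the communication, or access to it, at first prescription. That answer depends heavily on the HCP's own practice. Answers to the understanding items (Q14) may cluster too, though the reason is weaker.

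With positive correlation within HCP, 280 patient responses carry less information than 280 independent ones. Equation 1 then understates the uncertainty, and so will any simple binomial interval in the report. Sections 9.9 and 9.9.1 recognise that HCPs can influence patient results, but only as bias from highly compliant HCPs, never as a matter of variance.

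The code scheme makes this more than a question of analysis method. If no record shows which responses came through the same HCP, no later plan can compute a clustered variance. At stake is the honesty of the reported precision for the patient survey.

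**Working it through.** **Inputs from the Protocol.** n = 280, the 1.96 multiplier and the simple binomial variance (Section 9.5, Equation 1); at most 10 invitations per HCP (Section 9.2).

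**Inputs not in the Protocol, hence assumed.** Mean completed patient surveys per contributing HCP (m), and the ICC of an answer within HCP. Both are shown as ranges.

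**Step 1: reproduce Table 1.** Half-width = 1.96 × √(p(1−p)/280). For p = 50, 60, 70, 80 and 90% this gives 5.86, 5.74, 5.37, 4.69 and 3.51 points, which round to the printed 5.9, 5.7, 5.4, 4.7 and 3.5. The table is arithmetically correct for independent responses.

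**Step 2: possible number of clusters.** If every invitee of each contributing HCP responds, 280/10 = 28 HCPs suffice. With one responder each, 280 HCPs contribute. The Protocol does not place the study within that range.

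**Step 3: allow for clustering.** With equal cluster sizes:
- design effect DEFF = 1 + (m − 1) × ICC
- effective n = 280/DEFF
- half-width = Equation 1 half-width × √DEFF
- actual coverage of the nominal 95% interval = 2Φ(1.96/√DEFF) − 1

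Example, m = 5 and ICC = 0.10: DEFF = 1 + 4 × 0.10 = 1.40; effective n = 280/1.40 = 200; half-width at 50% = 5.86 × √1.40 = 6.93 points; coverage = 90.2%.

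| m | ICC | DEFF | Effective n | Half-width at 50% (points) | Coverage of nominal 95% CI |
|---|---|---|---|---|---|
| any | 0 | 1.00 | 280 | 5.9 | 95% |
| 2 | 0.05 | 1.05 | 267 | 6.0 | 94.4% |
| 2 | 0.10 | 1.10 | 255 | 6.1 | 93.8% |
| 3 | 0.10 | 1.20 | 233 | 6.4 | 92.6% |
| 5 | 0.10 | 1.40 | 200 | 6.9 | 90.2% |
| 10 | 0.01 | 1.09 | 257 | 6.1 | 94.0% |
| 10 | 0.10 | 1.90 | 147 | 8.1 | 84.5% |

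**Step 4: effect on the success criterion.** Sections 4.5 and 9.1 call the measures effective if most respondents show awareness, with no reference to a confidence limit. Clustering does not move the observed percentage, so that reading stands. Only a reader who looks at the lower limit would see a change, and only near 50%. At an observed 57% the simple limit is 57 − 5.8 = 51.2%. With DEFF 1.90 it is 57 − 8.0 = 49.0%.

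**Step 5: could it be corrected afterwards?** The patient survey asks for country but nothing that identifies the recruiting HCP or practice. Payment details, where given, belong to the patient and are stored apart from the answers (Section 9.6). The reporting list in Section 9.7 counts HCPs asked and invitations provided, but not HCPs whose patients responded. As written, even the number of clusters would be unknown.

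**The case against.** Several points on the other side are sound.

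- **Arbitrary choice is narrower than it may look.** A reader might infer that all patients are picked at the HCP's discretion. Section 9.2 confines this to HCPs with more than ten patients on the product; the others forward invitations to their patients. How many HCPs exceed ten is not stated.
- **Bias is not shown.** A reader might also infer that understanding will be overstated because HCPs favour engaged patients. That is possible, but nothing in the Protocol demonstrates it. Section 9.2 says HCPs are not asked to choose specific patients on eligibility grounds, and Section 9.9 already discloses a related bias.
- **Clusters may be small.** Packets also go to HCPs who have never prescribed the product, and Section 9.2 anticipates poor response. With about two responders per HCP and an ICC up to 0.10, the half-width is at most 6.1 points.
- **The primary objective is understanding.** The strongest case for clustering is receipt of the communication, not Q14.
- **Untracked codes are deliberate.** They protect anonymity and encourage candour.
- **The analysis plan may choose another interval.** Section 9.7 fixes no CI method.

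These points limit the size and the reach of the concern. They do not remove it. Without a cluster identifier, an analysis plan could only inflate intervals over guessed ICCs; it could not estimate the correlation, or show that clusters were small enough to ignore. Anonymity does not require discarding the grouping, because a number shared by up to ten codes identifies no patient.

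**Conclusion.** The point stands as one about precision and data collection. Randomly drawn HCPs each passing on up to ten invitations form a two-stage sample. Section 9.5 plans it as 280 independent responses, and Section 4.7 contradicts Sections 9.2 and 9.4 by calling the patients a random sample. If answers correlate within HCP, the Table 1 half-widths and the reported 95% CIs are too narrow for patients.

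The loss ranges from negligible (ICC 0.01, or one to two responders per HCP at ICC up to 0.10) to substantial (m = 10, ICC 0.10: 8.1 points instead of 5.9, coverage 84.5%). All of these figures rest on assumed m and ICC. The documents do not support saying that Table 1 is miscalculated, that the majority criterion would be wrongly met, or that understanding will be biased upward. The case for acting now is that the missing link cannot be recovered once responses are in.

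**What to change.** 1. **Section 9.4:** give the ten codes in each packet one anonymous packet number and store it with the response, with no link to patient or HCP identity. If paper surveys are used, print the same number on them.
2. **Section 9.7:** compute patient CIs with a cluster-robust variance at packet level, and report the number of packets that contributed responses.
3. **Section 9.5:** state that Table 1 applies to patients only under independence, and add half-widths over a range of design effects such as the one above.
4. **Section 4.7:** remove the description of patients as a random sample, in line with Section 9.4.
5. **Section 9.9:** list arbitrary selection by HCPs with more than ten patients on the product as a possible bias.

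The cost is a code-allocation table before mailing, a few lines of text, and somewhat wider patient CIs if correlation is present. Patients remain unidentified and non-responders untraceable.
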